3.0. Hypothesis

- Estrogen-containing methods, but not progestin-only methods, reduce the annual rate of pulmonary exacerbations, the microorganisms associated with a more rapid decline in lung function, and improve ppFEV1 (or absolute FEV1) of women with CF when compared to women with CF who use non-hormonal contraception (control group).
- Estrogen-containing oral methods of birth control are associated with higher incidence of gallbladder disease (defined as gallstones, requiring surgery), increased liver function enzyme values, and/or increased incidence of thromboembolism among women with CF.
- Both estrogen-containing and progestin-only hormonal methods improve BMI among women with CF, which is linked to nutritional status.
- The strength of agreement between DXA scan T-scores and CFFPR data about osteoporosis, osteopenia and bone fracture will be "substantial."
- The effectiveness of oral birth control is reduced compared to other methods of hormonal birth control in the presence of CFTR modulator use.
- Hormonal birth control use results in a greater proportion of patients with mucoid *Pseudomonas aeruginosa*, in patients who are *P. aeruginosa* positive, compared to non-hormonal contraceptive users.

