7.7. Sample Size

During the pilot phase, the study team will further discuss the statistical plan to ensure adequate numbers of participants are enrolled in the study. Based on information from participating centers, we expect to enroll approximately 600 women and expect about half of them to be on hormonal contraceptives based on our pilot study. The following table shows the power for detecting different RRs of non-hormonal to hormonal contraceptives in women and baseline proportion of outcome in the non-hormonal contraceptives group.

Table 8: Sample size calculation

	Using Poisson Regression Power to detect a Rate Ratio (hormonal / non-hormonal)
Total Sample Size	RR=0.70
450	0.77
475	0.80
500	0.82
525	0.83
550	0.85
575	0.86

CASE.4.CF Study Protocol

Recent data following the U.S. FDA approval of genetic modulators, show that in this population (mean age 25 years) there are approximately 0.8 PEx/year (13). Using Poisson regression, this study will have 80% power to detect a rate ratio of 0.70 between the progestin-only and combined hormonal groups with 575 enrolled women with CF (assuming alpha 0.05 and an estimated attrition rate of 15%). Although triple therapy has already been FDA approved, we do not anticipate this will affect our retrospective study design since we are evaluating years prior to FDA approval of triple modulator therapy.

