9.3. Statistical Methods

Because this is a retrospective cohort study, we are most interested in determining whether this exposure (to hormonal contraception) is associated with our primary outcome (counting the number of pulmonary exacerbations requiring additional IV in a given year) and/or our secondary outcomes (new respiratory microbiology, liver disease/non-cirrhosis, gallstone, requiring surgery/procedure, improved BMI, incidence of VTE, osteoporosis and fragile bone fracture). Women on hormonal contraception will be compared to the primary control group of women on non-hormonal contraception. We will also compare to women on no contraception, as the secondary control group. We will exclude persons with these existing diagnosis at the start of the follow up period for outcome data (January 1, 2010). Within this objective we will be able to calculate incidence rates, relative risks and confidence intervals. We will use Poisson regression to calculate progestin-only and combined hormonal method to non-hormonal method pulmonary exacerbation rate ratios and 95% confidence intervals. This allows for adjustment of follow-up time of each individual.

(Objective 1a): We will evaluate lab values over time (ppFEV1%, serum AST, ALT, alkaline phosphatase) to determine if trends between hormonal contraceptive users and non-hormonal contraceptive users differ. See Table 5 for confounders and covariates that we will use to adjust for the primary and secondary outcomes.

We will model ppFEV1 via generalized estimating equations (GEE), allowing for correlation within a subject, and compare via a fixed effect for exposure. Among women who change or stop contraception, we will estimate and compare within-participant difference in outcomes via the model (if numbers allow). We will censor women who switch method types or become pregnant, and for 6 months post pregnancy, for the primary analysis and subsequently follow them to leverage within-patient data and analyze changes in pulmonary status and contraception. Presence of respiratory microbiology will be estimated longitudinally via GEE with a logit link function. Graphic displays and summary statistics will be used; all *p* values will be two-sided.

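### The hypothesis that estrogen-containing but not progestin-only methods reduce exacerbations has no direct comparison of the two classes in 9.3 and no margin for concluding no reduction

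*Combined protocol and SAP*

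**What the plan says.** Section 3.0 lists first: "Estrogen-containing methods, but not progestin-only methods, reduce the annual rate of pulmonary exacerbations", with non-hormonal users as the control group. It asserts an effect for one class and the absence of an effect for the other.

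Section 9.3 gives the analysis: "We will use Poisson regression to calculate progestin-only and combined hormonal method to non-hormonal method pulmonary exacerbation rate ratios and 95% confidence intervals". It adds that "all *p* values will be two-sided". It does not list combined versus progestin-only, and neither 9.3 nor any other section gives a margin or a criterion for concluding no reduction.

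Section 7.7 points two ways. The column heading of Table 8 is "Power to detect a Rate Ratio (hormonal / non-hormonal", a pooled comparison. The text below the table says "this study will have 80% power to detect a rate ratio of 0.70 between the progestin-only and combined hormonal groups with 575 enrolled women", a comparison between the two classes. No power is given for progestin-only versus non-hormonal, which is the contrast behind the second half of the hypothesis.

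**The concern.** A statement that one class works and the other does not has two parts, and each needs its own evidence. A difference between classes needs the classes compared with each other. Absence of a meaningful reduction needs a confidence interval that rules one out. The two planned ratios supply neither by default. If the combined interval excluded 1 and the progestin-only interval included 1, the hypothesis would look confirmed, yet the two classes could have the same effect and differ only in group size. The progestin-only group is only part of the hormonal half, so its ratio is less precise than the pooled ratio in Table 8.

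Section 2.0 says the study is meant to help providers explain the effectiveness and safety of contraceptive methods to women with CF. A mistaken claim of class selectivity would feed directly into that advice.

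**Working it through.** **Inputs from the documents.** 7.7 gives 575 enrolled with 15% attrition, so 575 × 0.85 = 489 analysed. It says "there are approximately 0.8 PEx/year", gives a ratio of 0.70 and alpha 0.05 (two-sided in 9.3), and says of the approximately 600 women it expects to enrol that the investigators "expect about half of them to be on hormonal contraceptives based on our pilot study".

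**Inputs assumed.** Combined:progestin-only split from 50:50 to 80:20; person-years per woman T of 1, 3 or 5; between-woman dispersion d of 0, 1 or 2. None of these is in the documents.

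**Formula.** For a group of n women with rate λ × RR, the variance of the log rate is 1/(n λ RR T) + d/n. A log ratio has the sum of two such variances. Power is Φ(|ln RR|/SE − 1.96).

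**Table 8 first.** With two equal groups, 0.8 events per year, T = 1 and d = 0, power over the rows N = 450 to 575 is 0.87–0.93 without attrition and 0.81–0.89 with it. Table 8 prints 0.77–0.86. Equal groups with 0.61–0.63 events per woman reproduce it, and so, within 2 points, does 0.8 per year with 30% hormonal users and no attrition. The table may therefore be valid under unstated inputs and is not shown to be wrong. Both 0.63 and 0.8 are carried forward.

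**Progestin-only versus non-hormonal, true ratio 0.70, T = 1, d = 0, 0.8 per year.**
- Split 50:50 (244.5 versus 122.25 women): variance 1/195.6 + 1/68.46 = 0.0197, SE 0.140. Power Φ(0.357/0.140 − 1.96) = 0.72, so 28% missed.
- Split 80:20 (244.5 versus 48.9 women): variance 1/195.6 + 1/27.38 = 0.0416, SE 0.204. Power 0.42, so 58% missed.
- With 0.63 events the corresponding figures are 38% and 66%.

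**Both classes truly 0.70.** Three independent normal log rates were simulated. The misleading pattern is combined interval below 1, progestin-only interval not below 1. Ranges cover all splits and both event rates.

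| Follow-up and dispersion | Progestin-only effect missed | Misleading pattern |
|---|---|---|
| 1 year, d = 0 | 28–66% | 17–48% |
| 3 years, d = 0 | 1–23% | 1–23% |
| 5 years, d = 0 | 0–7% | 0–7% |
| 5 years, d = 1 | 20–52% | 13–44% |
| 5 years, d = 2 | 44–69% | 20–43% |

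Requiring the direct combined versus progestin-only interval to lie below 1 as well cuts the false claim to about 2.5% or less in every row.

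**Would the direct contrast be enough?** No. Take true ratios of 0.70 (combined) and 0.85 (progestin-only), so that both classes reduce exacerbations, with 0.8 per year and d = 0. Combined below non-hormonal and combined below progestin-only are both met in 40–76% of studies at 3–5 years. A rule that asks only for a progestin-only lower limit above 0.70 also fails: at 5 years it is met while the whole interval lies below 1 in 13–71% of studies. The conditions have to be joined.

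**The case against.** The strongest reply is that 9.3 reports 95% confidence intervals, not just p values. A progestin-only lower limit could already rule out a meaningful reduction, and 9.3 nowhere says it will read one significant and one non-significant ratio as confirmation. This stands. A reader might infer that non-significance is the only support the plan allows; the documents do not say so. What is missing is the margin against which the interval would be read.

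A reader might also infer a fixed, high error rate. That is not supported either. Outcome follow-up starts on January 1, 2010, registry data are requested to the most recent year, and the Poisson model adjusts for each woman's follow-up time. With several years per woman and little dispersion the problem nearly disappears. Against this, women with CF may differ in underlying exacerbation rate, and 9.3 censors switchers and pregnancies, which shortens person-time. The size is therefore open in both directions.

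Finally, 3.0 does not rank its hypotheses, the primary objective in 4.1 is the broader hormonal versus non-hormonal association, and 7.7 already mentions the between-class contrast. All true. But the mention in 7.7 shows that the contrast was intended, and 9.3 still does not plan it.

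**Conclusion.** The gap between the hypothesis and the analysis is in the text and needs no calculation: 3.0 makes a claim about two classes, 7.7 names the contrast between them, and 9.3 plans neither that contrast nor a criterion for no reduction. Its size is conditional. If both classes truly had a ratio of 0.70, the misleading pattern would arise in about 17–48% of studies at one person-year, 0–23% at 3–5 years under pure Poisson variation, and 13–44% at 5 years with dispersion 1–2. These figures assume 489 women, half non-hormonal, splits of 50:50 to 80:20 and 0.63–0.8 events per year. They illustrate the risk and are not properties of the plan. The point is worth acting on because the better analysis comes from a model already planned.

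**What to change.** In 9.3:
- Add the direct combined versus progestin-only rate ratio with its 95% CI, as a linear contrast from the planned Poisson model. Reconcile it with the contrasts named in the text and in Table 8 of 7.7.
- State that a difference between classes will be claimed only if this CI excludes 1.
- State that a reduction for estrogen-containing but not progestin-only methods will be claimed only if, in addition, the combined versus non-hormonal CI lies below 1, the progestin-only versus non-hormonal CI is not wholly below 1, and its lower limit lies above a margin that the investigators justify in advance.
- Otherwise report the progestin-only result as inconclusive.

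A margin of 0.70 is the most lenient choice, since it is the full design effect. With it, a true progestin-only ratio of 0.85 would still pass the joint rule in about 20–45% of studies at 3–5 years (combined 0.70, 0.8 per year, d = 0). The claim should therefore be worded as no reduction as large as the margin.

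The cost is a few lines and one contrast, with no new data. The downside is that a true hypothesis (0.70 and 1.00) is confirmed less often: with margin 0.70 at one person-year and d = 0, about 26–49% of the time, against 59–82% if significant versus non-significant were accepted. Power for these contrasts should be stated in 7.7 with the expected class split, person-years and dispersion.

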approved contraceptives has increased significantly since 2001, especially with the FDA-approval of hormonal longacting reversible contraceptive methods. In today's U.S. market, two types of hormonal contraceptives exist: estrogenand-progestin-containing methods (a.k.a. combined hormonal methods) and progestin-only methods. Within the estrogen-containing methods, contraceptive choices include oral pills and non-oral methods, such as the transdermal patch and vaginal ring. Within the progestin-only methods, contraceptive choices include four different hormonal intrauterine devices (IUD), a subdermal implant, a 3-month injectable depo-medroxyprogesterone acetate (DMPA), and progestin-only oral pills

The most recent edition of the national contraceptive guidance for women with medical conditions called the United States Medical Eligibility Criteria for Contraceptive Use (USMEC), was released in 2016 by the Centers for Disease Control and Prevention (CDC), which lists CF as a chronic health condition (6). The USMEC lists all hormonal methods safe to prescribe without restrictions (USMEC = 1), except the 3-month injectable, depot-medroxyprogesterone acetate (DMPA). DMPA is listed as USMEC = 2, in which the advantages of using the method in a woman with CF generally outweighs the theoretical or proven risks because of concerns about DMPA on bone health. Despite these national recommendations, the data for women with CF and hormonal contraception are limited. Potential complications for CF patients include decreased pulmonary function, CF-related diabetes (CFRD), CFLD, increased gallbladder disease, decreased nutritional status, increased venous thromboembolism and poor bone health. There are theoretical concerns that hormonal contraception may adversely impact these complications. Another concern is the reduced efficacy of hormonal contraception, specifically oral contraceptive pills with concomitant use of CFTR modulators.

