The definitions for normal bone, osteopenia, and osteoporosis are based on bone mineral density (BMD) scores. BMD is measured by dual energy X-ray absorptiometry (DXA), which provides both T-scores and Z-scores. These scores are used to define whether a person is categorized as having osteoporosis, osteopenia, or normal bone. According to the World Health Organization (WHO), the T-score is the number of standard deviations (SD) above (+) or below (-) the mean BMD in a young, normal, sex-matched population and is preferred for postmenopausal women. The Z-score is the number of standard deviations (SD) above (+) or below (-) the mean bone density in a normal, sex- and age-matched population and is preferred in females prior to menopause (7). In contrast to WHO criteria, the CFF uses Z-scores for children less than 18 years, considers T- and Z-scores as nearly equivalent for persons between ages 18-30 years, and uses T-score findings for persons with CF ages 30 years and older (8).

Our project is specifically designed to collect more information on these critically important issues by expanding our pilot contraceptive CFFPR study and further assess the safety and efficacy of contraception among patients with CF. With pilot funding from the Society of Family Planning, Drs. [name], [name], and [name] collaborated with two other CF centers to assess feasibility, data completeness, and data accuracy of a pilot contraceptive registry. Having successfully linked women with CF's self-reported information on current and prior contraceptive use with clinical data information obtained from the CFFPR, we are now ready to expand our work to include seven additional CF Centers for a total of ten centers (see Table 2).

The research questions we aim to answer for women with CF, aged 18-45 years in this retrospective study include:

- (1) Are estrogen-containing or progestin-only hormonal contraceptives associated with improved objective pulmonary symptoms compared to women with CF who use non-hormonal methods (control)?
- (2) Are estrogen-containing or progestin-only hormonal contraceptives associated with increased incidence of CFrelated liver disease (as noted with increasing trend of liver enzyme tests), gallbladder disease or thromboembolism?
- (3) Are estrogen-containing or progestin-only hormonal contraceptives associated with increased serum glucose trends (as measured by oral glucose tolerance testing) compared to women using non-hormonal methods?

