4.2. Secondary Study Objectives/Endpoints

- To assess the association of hormonal contraceptive use on trends in lung function (FEV1) over time, compared to non-hormonal contraceptive users (primary control) and non-contraceptive users (secondary control).
- To assess the association of hormonal contraceptive use on the incidence of venous or arterial thromboembolism.
- To assess the association of hormonal contraceptive use on prevalence of liver dysfunction, defined as gallstones (requiring surgery), hepatic steatosis, hepatic cirrhosis, and/or incidence of increased liver enzyme test values (ALT/GGT). Increased liver enzymes is defined as exceeding upper limit of normal on at least 3 occasions over 12-month period.
- To assess the association of hormonal contraceptive use on serum glucose trends, incidence of insulin resistance or time to CF-related diabetes (requiring insulin treatment).

- To assess association of hormonal contraceptive use on nutritional status through the evaluation of BMI trends.
- To validate bone health information in CFFPR with chart data obtained from one CF center (limited due to need for data use agreements between institutions for EMR data).
- To determine if those using hormonal contraception while using CFTR modulators report higher rates of unintended pregnancy compared to those taking non-hormonal contraception.
- To assess proportion of mucoid *P. aeruginosa*, in patients who are *P. aeruginosa* positive, among hormonal contraception users compared to non-hormonal contraceptive users.

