8.0. Methods: Assignment of interventions

8.1. Allocation

Participants will belong to a group based on their choice of contraception. Women with CF will be allocated to hormonal group (intervention), non-hormonal groups (control), and never used contraception.

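### The gallbladder, liver-enzyme and thromboembolism hypothesis names oral estrogen methods, but no planned comparison isolates them

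*Combined protocol and SAP*

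**What the plan says.** The second hypothesis in section 3.0 reads "Estrogen-containing oral methods of birth control are associated with higher incidence of gallbladder disease", and the same sentence adds raised liver enzymes and thromboembolism. The route looks deliberate. The first hypothesis in that section speaks of estrogen-containing methods without a route, and a later one sets oral methods against other hormonal methods. Section 2.0 makes clear that route and class differ: "Within the estrogen-containing methods, contraceptive choices include oral pills and non-oral methods, such as the transdermal patch and vaginal ring".

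The rest of the plan defines exposure for these outcomes in two ways:

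- **One hormonal group.** The thromboembolism objective in section 4.2 is "To assess the association of hormonal contraceptive use on the incidence of venous or arterial thromboembolism", and the liver and gallstone objective there uses the same exposure. Section 8.1 says "Women with CF will be allocated to hormonal group (intervention), non-hormonal groups (control), and never used contraception". Section 9.3 lists liver disease, gallstones and thromboembolism among the secondary outcomes and says "Women on hormonal contraception will be compared to the primary control group of women on non-hormonal contraception". It compares liver laboratory trends between the same two groups.
- **Two hormonal classes.** Research question 2 in section 2.0 asks "Are estrogen-containing or progestin-only hormonal contraceptives associated with increased incidence of CFrelated liver disease", and continues to gallbladder disease and thromboembolism. The exposure column of Table 5 (section 7.5) names combined and progestin-only contraception. Section 9.3 estimates separate ratios for the two classes, but only for pulmonary exacerbations.

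Neither definition separates oral from non-oral estrogen methods.

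**The concern.** A hypothesis about one type of method needs an estimate for that type. Here the nearest estimates are for all hormonal users, or at best for all combined users. Neither answers the stated question, whatever the true effects are.

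These are safety outcomes, and section 2.0 lists oral pills among the most commonly reported methods in the earlier survey. If a raised risk sits mainly with oral estrogen, a pooled result close to 1 could be reported as no association with hormonal contraception and then read as reassurance about the pill. The analysis would not support that reading.

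**Working it through.** **Matching the hypothesis to the comparisons**

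| Place | Exposure | Oral estrogen isolated? |
|---|---|---|
| 3.0, second hypothesis | Oral estrogen-containing methods | Yes (the claim) |
| 2.0, research question 2 | Estrogen-containing or progestin-only | No |
| 4.2, thromboembolism and liver objectives | Any hormonal use | No |
| 7.5, Table 5 | Combined and progestin-only | No |
| 8.1 | One hormonal group | No |
| 9.3, comparison for secondary outcomes and liver trends | Any hormonal use | No |
| 9.3, Poisson model | Combined and progestin-only, exacerbations only | No |

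This comparison alone establishes the mismatch.

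**Illustrating the consequence.** The plan has no figure to reproduce. It gives no event rate, effect size or power for these outcomes, and no share of users by method. The inputs below are assumptions.

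Let f be the share of hormonal use that is oral combined. Take a ratio of 2.0 for oral combined and 1.0 for every other hormonal method.

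Pooled ratio = 1 + f × (2.0 − 1) = 1.3, 1.5 and 1.7 for f = 0.3, 0.5 and 0.7.

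For information, take equal hormonal and non-hormonal groups and rare events, and set control events to 1 unit. Then var(log ratio) is proportional to 1/control events + 1/exposed events.

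- Pooled contrast: exposed events = 1 + f, so variance = 1 + 1/(1 + f).
- Separate contrast: exposed events = 2f, so variance = 1 + 1/(2f).
- Information ratio, separate to pooled = (ln 2 / ln(1 + f))² × pooled variance / separate variance.

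| f | (ln 2 / ln(1 + f))² | Pooled variance | Separate variance | Information ratio |
|---|---|---|---|---|
| 0.3 | 6.98 | 1.769 | 2.667 | 4.6 |
| 0.5 | 2.92 | 1.667 | 2.000 | 2.4 |
| 0.7 | 1.71 | 1.588 | 1.714 | 1.6 |

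**Power.** Section 7.7 gives 575 women with 15% attrition: 575 × 0.85 = 488.75, about 489, or 244.5 per group if half are hormonal users. Assume a 5% baseline risk and a ratio of 2. Power = Φ((|p1 − p0| − 1.96 × SE0)/SE1), two-sided alpha 0.05, with SE0 the standard error under a common risk and SE1 that under the assumed risks.

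| f | Pooled contrast | Oral combined vs non-hormonal |
|---|---|---|
| 0.25 | 0.09 | 0.34 |
| 0.50 | 0.21 | 0.45 |
| 0.75 | 0.37 | 0.51 |

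Using SE1 in both places leaves the pooled column unchanged to within 0.01 and lowers the last column to 0.23, 0.37 and 0.48. At a 1% baseline the first method gives 0.04, 0.07 and 0.11 pooled against 0.14, 0.15 and 0.15 separate. The separate contrast does better in each case, but power is never high.

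**The case against.** Several points on the other side have force.

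First, a reader might infer that the plan uniformly merges combined with progestin-only methods for these outcomes. It does not. Research question 2 covers exactly these outcomes and names both classes, and Table 5 lists both as exposures in a table that includes the thromboembolism and liver rows. The documents are inconsistent on class. Under the Table 5 split, only patch and ring users dilute the oral estimate. If oral methods were 80% to 90% of combined use (an assumption), a ratio of 2.0 would become 1.8 to 1.9.

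Second, a reader might infer that the other hormonal methods are believed to be free of these risks. The documents do not say so. Section 2.0 voices concern about hormonal contraception in general, and research question 2 includes progestin-only methods. A broad hormonal objective is consistent with that rationale, and the ratio of 1.0 used above is only an assumption. If other methods also carry risk, the dilution is smaller.

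Third, squaring the ratio of logs alone suggests that pooling costs a factor of 7.0, 2.9 or 1.7. That overstates the loss, because isolating oral users also shrinks the exposed group.

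Fourth, splitting the groups does not make a null result reassuring. With rare events in roughly 490 to 600 women, either contrast can easily miss a doubling of risk.

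Finally, section 6.0 says the analysis plan will be refined during the pilot phase, and the survey loses no method detail. That makes the gap easy to close, but it does not supply the missing contrast.

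**Conclusion.** The point holds in this form: section 3.0 states a hypothesis about oral estrogen methods, and no planned comparison tests it. The plan is silent on route everywhere outside the hypotheses, and inconsistent on class for these outcomes. This conclusion rests on the text alone and needs no assumption about effects.

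The size of the consequence is illustrative. With ratios of 2.0 and 1.0, equal hormonal and non-hormonal groups, rare events and oral combined shares of 30% to 70%, the pooled ratio falls to between 1.3 and 1.7, and the separate contrast carries about 4.6 to 1.6 times the information. None of those inputs is in the documents. The outcomes are secondary and the remedy is cheap, so this should be corrected but does not threaten the primary analysis.

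**What to change.** In section 9.3, and to match in 4.2, 8.1 and Table 5, define exposure for the gallbladder, liver and thromboembolism outcomes in four categories: oral combined, non-oral combined, progestin-only and non-hormonal. Make oral combined versus non-hormonal the test of the section 3.0 hypothesis, reported with a confidence interval. Keep pooled hormonal versus non-hormonal as a secondary comparison, and report the non-oral combined group descriptively if it is sparse. Section 9.3 also censors women who switch method types without defining a type, so state whether a change from pill to patch or ring counts as a switch.

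If the pooled or class-level comparison is what the investigators intend, reword the hypothesis to match it and draw no conclusion about oral estrogen from the result.

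The cost is analysis-plan wording. The survey in section 9.1.3 (Table 10) already collects each method used since 2008 with start and stop dates or ages, so no new data are needed. The drawback is smaller exposure groups and power that remains modest for rare events.
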